7.2. Definition of participants

Patients were included according to the indications and contraindications described in the use plan. Because of practical reasons (such as younger patients, participation in a number of clinical studies, alcohol/drug dependence patients, and other factors that may affect the completion and/or reliability of Ultrasound Endoscopy) and ethical reasons (whether informed consent can be completed, etc.), the entry and discharge criteria have been reduced.

7.3. Adverse events

The relevant definitions of adverse events are as follows:

Adverse Events (AE): Any adverse medical event, unexpected disease or injury, or adverse clinical manifestations (including abnormal laboratory findings) that occur in a subject, user or other person, whether or not associated with medical devices.

Serious Adverse Events (SAE): Adverse Events with the following information:

- causing death.
- leading to severe deterioration of the health of the subjects, including
- leading to life-threatening diseases or injuries,
- Causing impairment of body structure or function.
- Need hospitalization or extended hospitalization
- lead to hospitalization and preventive medical or surgical intervention
- Permanent damage to body structure or function
- Fetal distress, fetal death or congenital abnormalities or congenital defects.

Note: Hospitalization for existing conditions, or surgery required in the program, without serious deterioration of health status, is not considered a serious adverse event. Purposeful hospitalization, such as economic or reimbursement reasons, is not considered a serious adverse event.

Unexpected adverse device response (UADE): refers to adverse events related to medical devices that were not previously identified in the current version of the risk analysis report in terms of nature, severity or incidence. The definition includes any event caused by insufficient or inadequate description of the use or deployment of the device. This definition includes any event caused by a user's error.

7.4. Expected and trial-related adverse events

Previous studies have shown that the expected adverse events are basically the same as the complications of conventional endoscopic diagnosis and treatment.

The instrument used in this experiment is a medical software which is not in contact with

human body. There is no difference between the experimental operation and the routine operation. The intervention measures (such as randomized process) in the experiment may slightly increase the incidents of diagnosis and treatment.

7.5. Risk minimization

In this study, when the software malfunctioned, novice doctors and experts could still operate under their own judgment without affecting the routine treatment measures, and when the judgment of the two did not agree, the expert results prevailed, which greatly reduced the risk of the trial.

7.6. Related benefits

In this study, novice endoscopists were assisted by a deep learning-based bile duct sweep system to identify common bile duct stones. The AI-based technology allows novice ultrasound endoscopists to obtain diagnostic quality equivalent to that of experts with minimal training, helping to detect common bile duct stones in a timely manner and improve their diagnostic accuracy for common bile duct stones, alleviating the current shortage of experienced endoscopists and enabling early diagnosis and precise treatment of patients.

7.7. Overall feasibility analysis

The deep learning-based bile duct scanning system is an independent system including both software and computer hardware, which can monitor image data 24 hours a day. The system is not invasive. The overall operability is strong.

8. Statistical Analysis

8.1. Statistical Analysis Plan

Data management and statistical analysis were implemented by Renmin Hospital Wuhan University.

8.2. Methods

- 1) Means and standard deviations for continuous variables with equal distribution and medians for non-equal distribution; percentages for categorical variables.
- 2) Continuous variables were compared by t-test (e.g., age) or Mann-Whitney U test (bilirubin, aspartate aminotransferase, alkaline phosphatase, alanine aminotransferase).
- 3) Categorical variables were compared using McNemar's test.

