Study Process:	Determination of entry and exclusion criteria was performed before performing ultrasound endoscopy, and subjects who met all entry criteria and did not meet all exclusion criteria were included in the study. All patients who met the entry-exclusion criteria were randomized 1:1 into two groups A and B for a tandem, randomized controlled trial. Patients in group A were first swept by the novice endoscopist with the assistance of a deep learning-based bile duct sweep system during the examination, and then re-swept by the specialist without AI assistance after the sweep was completed; patients in group B were first swept by the specialist without AI assistance during the examination, and then swept by the novice endoscopist with AI assistance after the sweep was completed. Novice physicians and specialists were unaware of each other's sweeps, and subjects were unaware of their grouping. The recorder recorded the bile duct sweep results of the novice physicians and specialists during the 2 examinations in real time, and the patients were still to be followed up for 6 months after the procedure (telephone follow-up in months 1, 2, 3, and 6 with instructions to review liver function and abdominal ultrasound), and the end of the follow-up was the end of the study; the results of the collected patient examinations were transmitted to an independent data analysis group for review, and the review group was unaware of the subgroup of subjects.
Security:	Safety incidents shall be evaluated and reported according to the quality management measures for clinical trials of medical devices

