1.1 Time and Event Tables

Events	Screening period (d -30~0)	The day of Ultrasound Endoscopy (d 0)	Follow up ((d 0~180)
Informed Consent	X		
Basic characteristics	X		
Medical history/surgical history	X		
Physical Examination	X		
Inclusion/Exclusion Criteria		X	
Ultrasound Endoscopy		X	
Concomitant treatment	X	X	
Concomitant medication	X	X	
Adverse Events		X	X
Follow-up results (6 months)			X
Research completed			X

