3.1. Inclusion criteria

All patients meeting the following criteria will be considered for participation in the study:

- 1) Males and females aged 18 years and older who are suspected of having common bile duct stones at intermediate to low risk, where intermediate-risk patients are those with normal liver function but with abdominal ultrasound suggestive of bile duct dilatation, and low-risk patients are those with normal abdominal ultrasound and liver function but whose physicians still suspect common bile duct stones;
- 2) Able to read, understand and sign an informed consent;
- 3) The investigator believes that the subjects can understand the process of the clinical study, are willing and able to complete all study procedures and follow-up visits, and cooperate with the study procedures.

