4.2. Secondary Endpoints

- 1) Sensitivity, specificity, NPV, and PPV for the diagnosis of common bile duct stones in low and intermediate risk patients
- 2) Detection rate of gallstone lesions
- 3) Missed detection rate of gallstone lesions
- 4) Detection rate of bile duct lesions(all bile duct lesions including gallstones)
- 5) Missed rate of bile duct lesion(all bile duct lesions including gallstones)
- 6) Number of bile duct standard station scans
- 7) Scan time

Incidence of Adverse Events

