6.3.3. Intraoperative Managements

- 1) Subject position: lateral recumbent position with appropriate restraint.
- 2) Insertion route: chosen according to the subject's actual condition, usually transoral.
- 3) Bile duct sweep with novice followed by expert or expert followed by novice depending on the grouping.
- 4) Intraoperative abnormal findings must be scrutinized through standard clinical procedures, and photographs must be kept for documentation of any findings during ultrasound endoscopy.

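### Section 8.2 names McNemar's test for every categorical variable, but it is not valid for categories with one value per patient, such as adverse-event incidence

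*Combined protocol and SAP*

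**What the plan says.** Section 8.2 has three items. Item 1 covers description and gives percentages for categorical variables. Item 2 covers continuous variables: "Continuous variables were compared by t-test (e.g., age) or Mann-Whitney U test". Its examples are age, bilirubin and three liver enzymes. Item 3 covers categorical variables: "Categorical variables were compared using McNemar's test". Item 3 has no qualifier, and no other categorical test appears anywhere in the document.

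On design, the Summary (Study Process) says patients are "randomized 1:1 into two groups A and B". Section 6.3.3 describes what differs between the groups: "Bile duct sweep with novice followed by expert or expert followed by novice depending on the grouping". Every patient therefore has both sweeps, and A and B differ in their order.

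On the data, Section 4.2 lists "Incidence of Adverse Events" among the secondary endpoints. Section 1.1 schedules "Basic characteristics" at screening. Section 3.1 admits patients in two risk classes, and Section 6.3.4 has sedation status recorded.

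**The concern.** McNemar's test compares two readings of the same unit, using the pairs in which the readings disagree. The tandem design supplies such pairs for the binary novice+AI and expert results.

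It does not supply them for facts about the patient. Risk class, sedation status and categorical baseline characteristics have one value per patient. So does adverse-event incidence: the protocol defines no reader-specific adverse-event value, and Section 1.1 collects events both on the day of endoscopy and through follow-up to day 180. A comparison of these variables between groups A and B is a comparison of independent samples.

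Item 2 suggests that comparisons of this kind are intended. Its examples describe the patient, not the reader, and Mann-Whitney U is an independent-samples test. Item 3 is the parallel rule for categorical data, yet it offers only a paired test.

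At stake are any p-values reported for adverse events or categorical baseline variables. An analyst held to item 3 has no valid named test for them.

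**Working it through.** **Inputs from the documents.** Section 8.3 gives 147 patients, 20% dropout, 184 in total and two-sided 5% significance. Allocation is 1:1 (Summary, Study Process).

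**Assumption.** The documents give no prevalence for any patient-level category. A range is used, with the same prevalence p in A and B.

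**Group sizes.** 147 / (1 − 0.20) = 183.75, rounded up to 184, which matches the plan. Then 184 / 2 = 92 per group, or about 73 per group if 147 are evaluable.

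**Route 1: the group-by-category table is entered as if it were paired.** Let xA and xB be the numbers with the feature among n patients in each group. The off-diagonal cells are b = n − xA (A without the feature) and c = xB (B with it). The statistic is (b − c)² / (b + c), referred to 3.84.

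The null is E(b) = E(c), so n(1 − pA) = n·pB, which gives pA + pB = 1. The null of interest is pA = pB. The two coincide only when both proportions are 50%.

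With pA = pB = p, the statistic at the expected counts is n(1 − 2p)². For n = 92:
- p = 0.05: b = 87.4, c = 4.6, and 82.8² / 92 = 74.5
- p = 0.30: b = 64.4, c = 27.6, and 36.8² / 92 = 14.7
- p = 0.40: b = 55.2, c = 36.8, and 18.4² / 92 = 3.68
- p = 0.50: b = c = 46, and the statistic is 0

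Rejection rates under A = B, by exact enumeration of two independent binomials:

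| p | McNemar exact, n = 92 | McNemar uncorrected, n = 92 | McNemar exact, n = 73 | Pearson, n = 92 | Fisher, n = 92 |
|---|---|---|---|---|---|
| 0.02 | 100% | 100% | 100% | 3.7% | 0.4% |
| 0.05 | 100% | 100% | 100% | 4.2% | 1.9% |
| 0.10 | 100% | 100% | 100% | 5.1% | 2.7% |
| 0.30 | 99.6% | 99.8% | 97.9% | 5.1% | 3.4% |
| 0.40 | 42.2% | 48.1% | 30.4% | 4.9% | 3.5% |
| 0.50 | 0.4% | 0.6% | 0.4% | 4.6% | 3.2% |

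The pattern is symmetric about 50%: at 70% and n = 92 the exact version again rejects 99.6% of the time. The rate at 50% falls well below 5% because the variance of b − c is 2 × 92 × 0.25 = 46, while the test takes it to be b + c, about 92. The same null hides real differences that straddle 50%: with pA = 0.30 and pB = 0.70, the uncorrected test rejects 0.04% of the time.

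**Route 2: A and B patients are paired arbitrarily, for example by entry order.** At n = 92 under A = B, the exact version rejects 0.4% of the time at p = 0.02, 2.0% at 0.05, 2.9% at 0.10 and 3.6% at 0.50. The uncorrected version gives 3.8%, 4.4%, 4.9% and 5.0%. The size is acceptable, but the p-value depends on pairs that the design does not contain.

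**The case against.** The strongest reply is that the plan states no unpaired categorical test. The comparison it specifies is novice+AI against expert on the same patient, and McNemar's test suits that structure. Section 8.2 names neither sex, risk class nor sedation status, and nothing says that adverse events are tested between A and B. Item 1 allows percentages alone. Item 2 does not say which groups it compares; stone status or risk class would also be possible. All of this stands. It does not remove the defect, because those other groupings would be independent too, and item 3 has no exception for unpaired data.

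A reader might infer that the plan, followed as written, will almost always declare equal groups different. The documents do not support that. The near-certain rejection belongs to Route 1, a misuse that the plan does not describe, and to categories well away from 50%. An analyst who found no pairs might well choose some other, unspecified test. Nor can sex or risk class be assumed uncommon: near 50%, Route 1 hardly ever rejects.

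The loss of power carries little weight for baseline variables, since randomisation leaves no systematic A–B difference to detect. For adverse events, the documents give no basis for expecting a difference such as 30% versus 70%.

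**Conclusion.** The point holds as a minor one. Item 3 assigns a paired test to all categorical variables. That is wrong for those with one value per patient, including a listed safety endpoint, and no valid test is named for them.

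The size depends on how the rule is carried out. With 92 per group and A = B, false positives under exact McNemar run from 100% (2–10% prevalence) to 0.4% (50%) if the group table is entered, and stay at or below about 5% under arbitrary pairing. If these variables are only described, no p-value is affected. All the rates rest on assumed prevalences and on an A-versus-B comparison that item 2 suggests but the plan does not state.

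The primary endpoint and the other binary results paired within patient are untouched by this defect.

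**What to change.** Reword item 3 of Section 8.2 as two rules:

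- McNemar's test applies only to binary results recorded for both readers on the same patient.
- For categories with one value per patient, including adverse-event incidence, any comparison of groups A and B uses chi-square or Fisher's exact test. Alternatively, they are summarised by group with exact 95% confidence intervals and no test.

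The plan should say which of the two options in the second rule applies. At 92 per group and prevalences of 1–50%, the enumeration puts the false-positive rate at no more than about 5% for Pearson and below 4% for Fisher. The change needs no new patients, data or procedures. Its only cost is a second named method for categorical data.

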8.3. Sample Size Calculation

For the sample size determination, the level of bilateral significance was 5% ($\alpha=5\%$), 80% certainty ($\beta=20\%$), and based on previous reports of 90% diagnostic accuracy of endoscopists for common bile duct stones, a non-inferiority test of novice combined with AI non-inferiority to expert was performed, and a total of 147 patients were calculated to be enrolled. Assuming a 20% shedding rate, a total of 184 subjects were expected to be enrolled.

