Primary Endpoint:	Accuracy of diagnosis of common bile duct stones in patients with low and intermediate risk by novice combined with AI-assisted and expert
Secondary Endpoints:	1) Sensitivity, specificity, NPV, and PPV for the diagnosis of common bile duct stones in low and intermediate risk patients 2) Detection rate of gallstone lesions 3) Missed detection rate of gallstone lesions 4) Detection rate of bile duct lesions(all bile duct lesions including gallstones) 5) Missed rate of bile duct lesion(all bile duct lesions including gallstones) 6) Number of bile duct standard station scans 7) scan time 8) Incidence of Adverse Events
Trail design:	Single center, prospective, tandem, randomized control
Participants:	Male and female subjects aged 18 years and older at low to moderate risk of suspected common bile duct stones are required to undergo ultrasound endoscopy, voluntarily provide endoscopic imaging and sign an informed consent form
Sample size:	184 samples were collected to explore the sample distribution, and then calculate the sample size according to the sample distribution.

[figure not shown]

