4.1. Primary Endpoint

Accuracy of novice combined with AI-assisted and expert in the diagnosis of common bile duct stones in low to intermediate risk patients: ERCP and 6-month follow-up results as gold standard. A true positive was defined as CBD stones detected by EUS and the presence of CBD stones confirmed at ERCP; a false positive was defined as CBD stones detected by EUS and the absence of CBD stones confirmed by ERCP; a true negative was defined as CBD stones not detected by EUS and as CBD stones detected at 6-month follow-up; a false negative was defined as CBD stones not detected by EUS and subsequent ERCP or CBD stones were detected at 6-month follow-up.

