5.1. Purpose

The purpose of this study was to evaluate the effectiveness and safety of the proposed deep learning-based bile duct sweep system in improving the diagnostic accuracy of common bile duct stones and reducing the rate of missed gallstones during bile duct sweeps by novice ultrasound endoscopists through a single-center, tandem, randomized controlled trial.

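### The trial is sized for non-inferiority, but the plan gives no margin, no discordance rate and no decision rule, and the only test named for categorical outcomes tests equality

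*Combined protocol and SAP*

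**What the plan says.** The primary endpoint in section 4.1 is "Accuracy of novice combined with AI-assisted and expert in the diagnosis of common bile duct stones in low to intermediate risk patients". Each reader's result is classed as a true or false positive or negative, so it is correct or incorrect in each patient.

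Every patient is swept by both readers, and only the order is randomised. In group A the novice with AI goes first and the patient is "and then re-swept by the specialist without AI assistance after the sweep was completed" (section 1, Study Process). The primary outcome is therefore a paired binary one.

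Section 8.3 gives two-sided 5% significance, 80% power, 90% accuracy for endoscopists, 147 patients, 20% dropout and 184 enrolled. It states that "a non-inferiority test of novice combined with AI non-inferiority to expert was performed, and a total of 147 patients were calculated". On analysis, section 8.2 says only that "Categorical variables were compared using McNemar"'s test is used. Section 8.4 names the analysis sets for the primary endpoint but gives no success criterion.

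Three other places bear on this:
- Section 7.6 says the technology lets novices "obtain diagnostic quality equivalent to that of experts with minimal training".
- Section 5.1 gives the purpose as evaluating the system "in improving the diagnostic accuracy of common bile duct stones and reducing the rate of missed gallstones".
- The Sample size row of the Summary says that "184 samples were collected to explore the sample distribution, and then calculate the sample size according to the sample distribution".

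**The concern.** A non-inferiority conclusion needs a margin and a rule that compares the data with it, and neither is in the plan. McNemar's test suits the pairing but answers a different question. A non-significant result does not show non-inferiority, and a significant one does not rule it out. Its p-value also depends on how many pairs are discordant, so it can rank two results in the wrong order for this purpose.

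Without a margin fixed in advance, the tolerable loss of accuracy can be chosen after the results are known, and a claim that novices with AI match experts would not be confirmatory. Nor can a reader verify the 80% power: the margin and discordance are missing, and the 90% is given for endoscopists in general, not for novices with AI.

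**Working it through.** **Inputs from the documents:** two-sided 5% (taken as one-sided 2.5% for non-inferiority), 80% power, 90% accuracy, 147 evaluable, 20% dropout (all section 8.3).

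**Assumptions, because the documents give no figure:** no true difference between readers; discordance ψ of 5%, 10% or 18%. The last is what independent errors give at 90% accuracy: 2 × 0.9 × 0.1 = 0.18.

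**1. The plan's own figure.** 147 / (1 − 0.20) = 183.75, which rounds up to 184. The dropout step reproduces. The 147 cannot be reproduced, because the margin and discordance are missing. An unpaired calculation at 90% in both groups does not settle it either: from n per arm = 2 × 0.9 × 0.1 × (1.960 + 0.842)² / d², 147 per arm implies d = 9.8 points and 147 in total implies 13.9 points.

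**2. Margin implied by 147 pairs.** d = (1.960 + 0.842) × √(ψ/147):
- ψ = 0.05: 5.2 points
- ψ = 0.10: 7.3 points
- ψ = 0.18: 9.8 points

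**3. Power of 147 pairs.** The Wald approximation is Φ(d × √(147/ψ) − 1.960). The exact figures come from full enumeration of the trinomial distribution with the paired (Tango) score test.

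| Margin | Method | ψ = 5% | ψ = 10% | ψ = 18% |
|---|---|---|---|---|
| 5 points | Wald | 77% | 48% | 30% |
| 5 points | exact score | 62% | 43% | 28% |
| 8 points | Wald | 99% | 87% | 63% |
| 8 points | exact score | 95% | 80% | 60% |
| 10 points | Wald | >99% | 97% | 82% |
| 10 points | exact score | 99% | 94% | 79% |

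Depending on the missing inputs, 147 runs from badly underpowered to more than enough.

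**4. McNemar against a margin-based reading.** Take two illustrative results in 147 patients, with b = only the novice correct and c = only the expert correct. McNemar's z is (b − c)/√(b + c). The score limits are the values δ at which (b − c − 147δ) / √[147(2q + δ − δ²)] equals ±1.960, where q is the constrained estimate of the expert-only-correct probability.

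| b vs c | Difference | 95% score interval | McNemar p (exact p) |
|---|---|---|---|
| 9 vs 18 | −6.1 points | −13.4 to +0.9 | z = −9/√27 = −1.73, p = 0.083 (0.122) |
| 0 vs 6 | −4.1 points | −8.6 to −1.4 | z = −6/√6 = −2.45, p = 0.014 (0.031) |

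The non-significant result has the worse lower limit. For any margin between 8.6 and 13.4 points the first result fails non-inferiority and the second passes, the reverse of what the p-values suggest. Below 8.6 both fail; above 13.4 both pass.

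**5. If non-significance were read as success.** Suppose the true accuracies were 80% for novice with AI and 90% for expert (an assumption). By exact enumeration, uncorrected McNemar would be non-significant in 8%, 19% or 33% of trials of 147 at ψ = 15%, 20% or 26%. Here independent errors give 0.8 × 0.1 + 0.2 × 0.9 = 0.26.

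**The case against.** Section 8.2 is a short generic list. It does not tie McNemar's test to the primary endpoint, and nothing in the plan says that a non-significant result will be read as non-inferiority. On that view the power attaches to a non-inferiority test whose margin and method simply went unreported. Step 5 then measures a misuse that the plan does not prescribe, and the counts in step 4 are chosen to make the point. At a 10-point margin, 147 is adequate or nearly so across the whole discordance range. The benefits paragraph in section 7.6 is not a statement of hypothesis. Finally, requiring a score interval could itself lower the stated power: at 5 points and 5% discordance it falls from 77% to 62%.

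Much of this is fair on framing. The step 4 and 5 figures are illustrations, the 10-point figures belong in the picture, and any valid pre-specified paired interval would close the gap. None of it supplies the missing margin, inputs or criterion. McNemar's is still the only test offered for a categorical outcome.

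**Conclusion.** The concern holds and must be fixed. The primary comparison is a non-inferiority one, and the plan contains no margin, no paired assumptions and no rule for declaring it met; the test it names has the wrong null for that purpose.

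The sample size is unverifiable, not shown to be wrong. Under no true difference, exact power of 147 pairs runs from 28% (5-point margin, 18% discordance) to 99% (10-point margin, 5% discordance). These margins and discordances are assumptions.

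Two related inconsistencies are secondary, and the main point stands without them. The Summary describes a sample size still to be calculated, whereas section 8.3 reports a finished calculation; both give 184. Section 5.1 speaks of improving novice accuracy, but no sweep by an unaided novice exists against which improvement could be measured.

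**What to change.** 1. In section 8.3, state and justify the margin, the discordance and the expected accuracy of novices with AI that were actually used to reach 147. Do not adopt a value back-solved from 147. If none was recorded, set and justify them now. In either case, fix the margin before accuracy data are seen.
2. In section 8.2, define the primary analysis as the paired difference in accuracy (novice with AI minus expert) with a two-sided 95% paired score interval (Tango or Nam). Another valid paired interval would serve if pre-specified. Declare non-inferiority only if the lower limit lies above minus the margin. Say which analysis set the rule is applied to; section 8.4 currently makes per protocol the main one. Keep McNemar's test as secondary.
3. Check 147 against the stated inputs with the same interval method. If they do not give 80%, restate the power or re-derive N.
4. Reconcile the Sample size row of the Summary with section 8.3. Reword section 5.1, and the matching Expected effect row of the Summary, as a comparison of AI-assisted novices with experts.

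The cost is wording and a little analysis, with no added visits or procedures. Disclosure may reveal a wide tolerance or a less favourable power. Restating the power is the cheap option; enlarging N is not.
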